## 2. Glossary

Abbreviation	Term
ADE	Adverse Device Effect
AE	Adverse Event
AEAC	Adverse Events Advisory Committee
AGA	Activity Goal Assessment
AP	Anteroposterior Position
ASADE	Anticipated Serious Adverse Device Effect
CIP	Clinical Investigation Plan
CRF	Case Report Form
CRPS	Complex Regional Pain Syndrome
DD	Device Deficiency
DDD	Degenerative Disk Disease
DMC	Data Monitoring Committee
EC	Ethics Committee
eCRF	Electronic Case Report Form
ENS	External Neurostimulator
EQ-5D-5L	EuroQol Five Dimensions Questionnaire
FBS	Failed Back Syndrome
HD	High Dose
IC	Informed Consent
ICF	Informed Consent Form
ICH	International Conference on Harmonization
INS	Implantable Neurostimulator
IRB	Institutional Review Board
LTFU	Lost to Follow-up
MLTC	Multi-Lead Trialing Cable
NPU	Neuro Programmer Upload
ODI	Oswestry Disability Index
OUS	Outside US
PGIC	Patient Global Impression of Change
PMA	Pre-Market Application
RCT	Randomized Controlled Trial
RDC	Remote Data Capture
RSD	Reflex Sympathetic Dystrophy
SADE	Serious Adverse Device Effect
SAE	Serious Adverse Event

Abbreviation	Term
SAP	Statistical Analysis Plan
SCS	Spinal Cord Stimulation
SSA	Subject Satisfaction Assessment
US	United States
USADE	Unanticipated Serious Adverse Device Effect
VAS	Visual Analog Scale

Terms	Definitions
High Dose (HD) Stimulation	For the purposes of the Vectors Post Market study, HD stimulation is stimulation delivered at a pulse width of 90 – 200 µsec and 1000 Hz at a comfortable amplitude or intensity
Overall pain	The combination of low back and leg pain. For the purposes of this study, the HD stimulation responder rate, using the VAS for overall pain, will be compared against the performance goal
Painful Paresthesia	Uncomfortable or unexpected stimulation (e.g. jolting or shocking sensation experienced by the patient) due to excessive SCS therapy
Paresthesia	Tingling sensation typically generated by SCS therapy
Paresthesia Mapping	Test stimulation used to determine if area of stimulation overlaps with a subject's areas of pain
Perception threshold	The stimulation intensity at which the subject first perceives paresthesia
Visual Analog Scale	For the purposes of the Vectors Post Market study, the visual analog scale (VAS) will always be a single day score.

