**Table 1 SCS Dose**

Parameter	Medtronic Device Range	Description	Conventional	High Dose
Dose	Variable, based on settings	A product of pulse width, frequency, and current.  Reported in micro Coulombs per second ( $\mu$ C/sec), also referred to as Charge per second.	50 Hz, 400 $\mu$ sec, 4 mA = 80 $\mu$ C/sec	1000 Hz, 90 $\mu$ sec, 4 mA = 360 $\mu$ C/sec

SCS therapy relies on the delivery of energy to a specified stimulation spinal cord target. Conventional stimulation has targeted any area of the dorsal columns that result in a comfortable paresthesia perception over the painful area. HF10 therapy simplified SCS therapy by staggering two epidural leads along the midline from T8 to T11. The typical starting target for HF10 therapy is a bipole at the T9-T10 disc space. This is in accord with a study by Barolat et al. (1993), who determined that targeting the T9-T10 implanted “strictly midline” was the “best location” for SCS to treat low back pain without stimulation of the chest or abdominal wall. Barolat (2001) used conventional stimulation parameters at T9-T10 in which 68.8% of patients reported fair to excellent pain relief after 1 year of stimulation. In a recent study of HF10, the investigators placed two leads over the T9-T10 intervertebral space and reported that 84.5% of HF10 subjects were back pain responders, reporting greater than 50% pain relief.

While the patient outcomes with these stimulation parameters and location is promising, additional clinical research is needed to understand the amount of energy and the specific stimulation target that will result in the best patient outcomes.

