### **9.15.1. Single-day Visual Analog Scale (VAS)**

Pain will be assessed by a single-day VAS (0 – 100 mm). The VAS will be used to evaluate the primary and two secondary study endpoints with 0 mm meaning "no overall, low back, or leg pain" and 100 mm meaning "worst overall, low back, or leg pain imaginable." Subjects will be asked to report pain intensity "in the last 24 hours" by marking a line perpendicular to the VAS line at the point that represents their pain intensity. Site personnel will determine the score by measuring the distance (mm) on the 100-mm line between the left, "no pain" anchor and the subject's mark, measuring the total

distance of the line (to ensure that it is 100 mm) and dividing the distance from the “no pain” mark to the subject’s mark by the total distance of the line. The scored VAS ranges from 0 – 100. The VAS will be administered at the Baseline, Follow-up Visits (2-Week, 4-Week, 6-Week and 3-, 6- and 12-Month Visits), and Unscheduled Visits. The VAS data will be the basis for verification of certain study entry criteria at the Baseline Visit and for calculation of the primary study endpoint.

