### 13.1.3. Interim efficacy analyses

An interim analysis providing preliminary characterization of the secondary objectives will be performed in late 2018 with the intent of presenting the results in early 2019. The details of these analyses will be specified in the SAP.

Analyses of the efficacy outcomes and safety assessment will be performed after 100 subjects have reached the 3-Month Visit, as described in section 13.1.6. The primary efficacy objective will not be evaluated. These analyses will be specified in the SAP and are not intended to be used to modify the study.

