### 13.1.5. Multiple testing adjustment

The study has one primary objective that will be evaluated with statistical testing. The primary objective will be evaluated at an alpha level of 0.05 after all subjects in the Treated Analysis Set have completed the 3-Month Visit.

Therapy efficacy will be demonstrated by successfully passing the primary objective analysis. The secondary objectives are not alpha-controlled; they will be characterized but not evaluated with statistical testing.

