4.3. Secondary Objectives

1. To characterize the overall (low back and leg) pain efficacy responder rate, as measured by the VAS, from Baseline to the 3-Month Visit, with a confidence interval within $\pm 10\%$
2. To characterize the low back pain efficacy responder rate, as measured by the VAS, from Baseline to the 3-Month Visit, with a confidence interval within $\pm 10\%$
3. To characterize the leg pain efficacy responder rate, as measured by the VAS, from Baseline to the 3-Month Visit, with a confidence interval within $\pm 10\%$

[REDACTED]

5. Investigation Plan

[figure not shown]
This is a global, prospective, single-arm, multi-center, open label study evaluating the efficacy of SCS therapy for pain relief using HD stimulation parameters while targeting a specific anatomical location. The study will be conducted at up to 30 centers globally.

To be enrolled in the study, adult patients must have both low back and leg pain of at least 50mm (out of 100mm) on the Visual Analog Scale (VAS), and an Oswestry Disability Index (ODI) score from 21 to 80 (out of 100). They must be on stable pain medications for the treatment of their pain and be willing to not increase these medications through the 3-Month Visit.

Subjects who meet the inclusion and exclusion criteria at Baseline undergo a trial lead implant procedure. At Device Trial, if the final lead placement after paresthesia mapping spans the T9/T10 disc space, the subjects may continue in the study. Subjects using HD stimulation settings with a self-reported pain improvement of at least 50% at Day 2 or Day 4 of the trial are then eligible to receive a permanent SCS implant within the study.

Once implanted with a permanent SCS system, if the final lead placement spans the T9/T10 disc space, the subject continues in the study with the following visits: Device Activation, 2-Week, 4-Week, 6-Week, 3-Month (Primary and Secondary objectives visit), 6-Month, and 12-Month, with a planned phone call between each visit. Subjects will discontinue from the study following the 12-Month Visit. Figure 1 shows the study visits from Baseline through the 12-Month Visit.

Figure 1. Vectors PM study visit flowchart

6. Determination of Sample Size

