7.5. Adjustments for Multiple Comparisons

The study has one primary objective that will be evaluated with statistical testing. The primary objective will be evaluated with statistical testing at the $\alpha=0.05$ level after all subjects in the Treated Analysis Set have completed the 3-Month Visit. The secondary objectives are not alpha-controlled; they will be characterized but not evaluated with statistical testing.

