7.9.1.1. Hypothesis

The mean change in overall pain in implanted subjects (μ_c) from baseline to 3 months will be statistically significantly different from no change on the VAS scale 0-100 mm:

$$H_0: \mu_c = 0$$

$$H_A: \mu_c \neq 0$$

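### Does the glossary's mention of a performance goal leave the overall-pain responder rate facing an unspecified pass/fail comparison?

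*Protocol*

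**What the plan says.** Protocol section 2 (Glossary) defines overall pain as low back and leg pain combined, then adds that "the HD stimulation responder rate, using the VAS for overall pain, will be compared against the performance goal".

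The sections that set out the analysis read differently:

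- **Objective.** SAP 4.3, matching Protocol 5.1.3, lists as the first secondary objective: "To characterize the overall (low back and leg) pain efficacy responder rate". The low back and leg rates are the second and third.
- **Testing.** SAP 7.5 says: "The secondary objectives are not alpha-controlled; they will be characterized but not evaluated with statistical testing". The Protocol synopsis and Protocol 13.1.5 say the same.
- **Basis for an efficacy claim.** Protocol 13.1.5: "Therapy efficacy will be demonstrated by successfully passing the primary objective analysis".
- **Primary hypothesis.** SAP 7.9.1.1 concerns a mean change that "will be statistically significantly different from no change on the VAS scale 0-100 mm". It involves neither a responder rate nor a goal.

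A second small mismatch is in Protocol 9.15.1: "The VAS will be used to evaluate the primary and two secondary study endpoints". Protocol 5.1.3 and SAP 4.3 each list three secondary objectives, all measured by VAS.

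**The concern.** In a single-arm study, comparing a responder rate with a performance goal normally means a verdict: the rate clears the goal or it does not. The glossary speaks of the goal as though it were already defined, yet no number, source or rule can be found.

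Timing sharpens the worry. Protocol 13.1.3 plans a preliminary look at the secondary objectives in late 2018, "with the intent of presenting the results in early 2019". A goal chosen after that would be chosen with responder rates already known.

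The clause also speaks of an HD stimulation responder rate. The visible calculation in SAP 7.9.2.1 takes every subject in the Treated Analysis Set, with no condition on the settings in use at Month 3. If the clause were operative, both the threshold and the rate to be compared with it would need defining.

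**Working it through.** **Step 1: which rate does the glossary mean?** It is not the device-trial response. That is a self-reported percent improvement (Protocol 9.3 and 9.15.2), and Table 4 schedules no VAS at the trial visits. The glossary names the VAS for overall pain, so it means secondary objective 1.

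**Step 2: is a goal given elsewhere?** The visible text offers three percentages that might be mistaken for one:

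- Protocol 4.1 cites a 10 kHz study in which "84.5% of HF10 subjects were back pain responders". This concerns back pain and a different therapy, and is background only.
- The same section cites 68.8% with fair to excellent relief in a study of conventional stimulation. That is a different outcome definition, and again background.
- Protocol 13.4.1 and SAP section 6 use 50%, as the planning rate at which the interval is widest.

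None is called a goal. The ±10% in the secondary objectives is a limit on interval width.

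**Step 3: does the responder-rate sample size use a goal?** The inputs in Protocol 13.4.1 and SAP section 6 are confidence level 0.95, P = 0.5, Wilson score, two-sided. The half-width is

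h = z·√[p(1−p)/n + z²/(4n²)] / (1 + z²/n), with z = 1.96.

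For n = 100 and p = 0.5:

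- inside the root: 0.0025 + 3.8415/40,000 = 0.002596; the root is 0.05095
- numerator: 1.96 × 0.05095 = 0.09986
- denominator: 1 + 0.038415 = 1.038415
- h = 0.0962, giving 40.4% to 59.6%

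The plan states 9.6% and 40.4% to 59.6%, so it reproduces, as do the rows for 50 to 90 subjects. The ±10% target is first met at n = 93 (h = 9.96%; at n = 92 it is 10.01%). No null or goal rate enters.

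**Step 4: does the primary sample size use a goal?** The inputs in Protocol 13.3.4 are two-sided alpha 0.05, power 0.9, null mean 0, mean 20 and SD 30. One-sample t-test power comes from the noncentral t with noncentrality (20/30)·√n:

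| n | Noncentrality | Power |
|---|---|---|
| 25 | 3.33 | 0.892 |
| 26 | 3.40 | 0.904 |
| 100 | 6.67 | 0.999998 |

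The smallest n reaching 0.9 is 26, as stated, and power at 100 exceeds 99%, as stated. The null is a mean change of zero.

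**Step 5: compare the provisions.**

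| Element | Where | Goal used? |
|---|---|---|
| Secondary objective | Protocol 5.1.3; SAP 4.3 | No |
| Sample size | Protocol 13.3.4, 13.4.1; SAP 6 | No |
| Multiplicity | Protocol synopsis, 13.1.5; SAP 7.5 | No |
| Responder-rate analysis | Protocol 13.4.1; SAP 7.9.2.4 | No (visible text) |
| Interim looks | SAP 7.8 | No; no formal testing |
| Primary test | Protocol 13.3.2; SAP 7.9.1.1 | No |
| Glossary entry | Protocol 2 | Yes, undefined |

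The glossary stands alone against provisions that agree with one another. An analyst following the SAP produces the estimate and its interval and has no comparison to run.

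**Step 6: the count in Protocol 9.15.1.** That same paragraph gives scale anchors for overall, low back and leg pain, and Table 4 schedules all three scores. No endpoint would be lost by taking the sentence literally.

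**The case for a change.** The best case for acting is that the clause is current protocol text and that any verdict would hinge on the missing number. With goals assumed for illustration, because none is given, 50 responders of 100 (Wilson 40.4% to 59.6%) would clear a goal of 40% but not 45%. An exact one-sided 0.025 test at n = 100 with a true rate of 50% would have 98% power against a goal of 30% and 46% against 40%. A goal named after the interim presentation would be open to criticism.

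The textual mismatch stands. The rest does not carry it further:

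- The illustrative figures reflect the goals put in. They show what an unplanned comparison could do and reveal no defect in a planned one.
- Nothing visible suggests that a goal will be set later, and SAP 7.8 rules out formal testing at the interim looks.
- A purely descriptive remark beside a benchmark would not breach the no-testing statement, though it would need a named benchmark.
- The HD label has a plain basis. Treated subjects had a positive trial on HD parameters (SAP 7.1.3), and the primary objective speaks of HD as the starting setting. SAP 7.7 already identifies who received non-HD settings and when they first did. The rate over all Treated subjects is a valid HD-first result. Whether more is said about settings cannot be judged, because text after SAP 7.9.2.4 and Protocol section 13.4.4 are blacked out and cannot be counted as missing.

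**Conclusion.** No change to the plan follows. The performance-goal clause is a stray phrase in a definition, and the two-for-three count in Protocol 9.15.1 is a counting slip. Both are clerical and can be tidied whenever the Protocol is next revised.

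The effect is zero on the primary test, on the three responder rates and on their intervals. No corrected figure can be computed, because no stated figure depends on a goal.

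This rests on two assumptions. The first is that the analysis follows the SAP, which describes itself as comprehensive for the final report. The second is that the blacked-out text holds no goal. If it did, that goal would have to be reconciled with the visible statements in Protocol 13.1.5 and SAP 7.5 that this rate is not tested.

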### 3. Synopsis

Title	Vectors Post Market: A study to assess pain relief using spinal cord stimulation (SCS) with high dose (HD) stimulation parameters
Clinical Study Type	Post-Market study
Product Name	Medtronic RestoreSensor® SureScan® MRI and Intellis™ AdaptiveStim® Neurostimulation System
Global Sponsor	Medtronic, Inc. Medtronic Neuromodulation [name] U.S.A. [contact]

	
[REDACTED]

Study Design	
This is a global, prospective, single-arm, multi-center, non-randomized study evaluating the efficacy of SCS therapy for pain relief using HD stimulation parameters while targeting a specific anatomical location. The study will be conducted at up to 30 centers in the globally.

Sample Size	
Up to 215 subjects will be enrolled globally.

Inclusion/Exclusion Criteria	
Inclusion Criteria
 
 
1. Willing and able to provide a signed and dated informed consent
 
2. At least 18 years old at the time of enrollment
 
3. Candidate per labeling for an SCS system (trial and implant) as an aid in the management of chronic, intractable pain of the trunk and limbs (low back and leg pain)
 
4. Baseline VAS is <math>\geq 50</math> mm for low back pain
 
5. Baseline VAS is <math>\geq 50</math> mm for leg pain
 
6. ODI score of 21 to 80 out of 100
 
7. On stable (no change in dose, route, or frequency) pain medications (prescribed and over-the-counter) being used for back and leg pain, as determined by the investigator, for at least 28 days prior to enrolling in the study
 
8. Willing and able to attend visits and comply with the study protocol
 
9. Willing and able to not increase their pain medications (prescribed and over-the-counter) being used specifically for back or leg pain through the 3-Month Visit
 
 
Additional Inclusion Criterion (evaluated at Device Trial - Implant)
 
 
1. After paresthesia mapping to confirm proper location at Device Trial, final lead placement spans the T9/T10 disc space
 
2. After paresthesia mapping to confirm proper location at permanent implant, final lead placement spans the T9/T10 disc space
 
 
Exclusion Criteria

	
 
1. Previously trialed or implanted with spinal cord stimulator, peripheral nerve stimulator, or an implantable intrathecal drug delivery system
 
2. Expected to be inaccessible for follow-up
 
3. Subject is currently participating, or plans to participate, in another investigational study unless written approval is provided by the Medtronic study team
 
4. Current diagnosis of moderate to severe central lumbar spinal stenosis with neurogenic claudication, as determined by the investigator
 
5. Major psychiatric comorbidity or other progressive diseases that may confound study results, as determined by the investigator
 
6. Serious drug-related behavioral issues (e.g. alcohol dependency, illegal substance abuse), as determined by the investigator
 
7. Pregnant or planning on becoming pregnant (if female and sexually active, subject must be using a reliable form of birth control, be surgically sterile, or be at least 2 years post-menopausal)
 
8. Unable to achieve supine position
 

Study Procedures and Assessments
	
Specific data and procedure requirements per visit are summarized in Table 4.
 
Study Visits
 
 
• Baseline Visit
 
• Device Trial Day 0 – Lead Placement and initial programming
 
• Device Trial Day 2
 
• Device Trial Day 4 (if necessary)
 
• Device Trial Day 6 (if necessary)
 
• Implant
 
• Device Activation Visit
 
• 2-Week Visit
 
• 4-Week Visit
 
• 6-Week Visit
 
• 3-Month Visit
 
• 6-Month Visit
 
• 12-Month/Final Visit
 
 
Baseline Visit:                  Subjects are considered enrolled at the time the study-specific informed consent/HIPAA form (or other data protection authorization as required by local regulations) is signed. Subjects in compliance with inclusion/exclusion criteria will be eligible to participate. A VAS score for overall (low back and leg), back, and leg will be collected. Subjects that do not have a VAS <math>\geq</math> 50 mm for low back pain and VAS <math>\geq</math> 50 mm for leg pain will be exited from the study. Subjects that meet the pain inclusion criteria will be asked about their back and leg pain/surgical history, be scheduled for a device trial, and complete the required assessments (e.g., EQ-5D-5L, ODI, and activity goal).

	
Device Trial: Day 0 (≤ 14 days post Baseline Visit)                  At Day 0, subjects will be implanted with two percutaneous leads per labeling. Subjects who have leads spanning the T9/T10 disc space will continue in the study. In the recovery room, subjects who have electrodes over the T9/T10 disc space will be programmed with 1 HD programming configuration.
 
Device Trial Day 2: (2 – 4 days after Device Trial Day 0)                  The effectiveness of the stimulation parameters programmed at Day 0 will be assessed for 2 days. If a subject has ≥ 50% reduction in pain, they will have their trial leads explanted and proceed to implant. If a subject does not have ≥ 50% pain relief, they will be reprogrammed to the second HD group and return for a Day 4 Visit.
 
Device Trial Day 4, if necessary: (2 – 4 days after Day 2 Visit)                  The effectiveness of the stimulation parameters programmed at Day 2 will be assessed for 2 days. If a subject has ≥ 50% reduction in pain, they will have their trial leads explanted and proceed to implant. If a subject does not have ≥ 50% pain relief, they will be reprogrammed using any on-label parameters (physician preference) and return for a Day 6 Visit
 
Device Trial Day 6, if necessary: (2 – 4 days after Day 4 Visit; no later than Day 10)                  Subjects will return to the clinic a minimum of two days later to assess the effectiveness of the physician preference stimulation parameters programmed at Day 4 and have their trial leads explanted. These subjects will then be exited from the study.
 
Implant (≤ 30 days post end of device trial)                  Subjects who were HD responders during the device trial and who met all eligibility criteria will be implanted with a RestoreSensor SureScan MRI or Intellis AdaptiveStim neurostimulation system. Subjects will be implanted with two compact percutaneous leads per labeling. Subjects who have leads spanning the T9/T10 disc space will continue in the study. The stimulator will be “OFF” when the subject leaves this visit.
 
Device Activation Visit (9 – 16 days post implant) The Device Activation Visit will take place 9 – 16 days after implant, pending wound healing. The stimulator will be turned “ON” at this visit and the programming that was successful for the trial will be programmed for that subject.
 
Follow-up Visits (2 weeks, 4 weeks, 6 weeks ± 3 days and 3, 6, and 12 Months ± 15 days post Device Activation)                  Visits will occur at weeks 2, 4 and 6 and months 3, 6 and 12 post device activation. EQ-5D-5L, ODI, PGIC, and SSA will be assessed at 3-, 6- and 12-Months. The VAS

--	--

	
will be administered at all follow-up visits and scored by site personnel. The Paresthesia Assessment and Recharging Questionnaire will be collected at the 3- and 12-Month Visits. The Activity Goal will be completed through the 3-Month Visit. Data for the primary endpoint will be collected at the 3-Month Visit.
 
Telephone Calls (Daily during Device Trial, Monthly post Device Activation) Subjects will be called 1, 3, 5, 7, 8, 9, 10 and 11 weeks post-device activation to assess their pain relief status and then monthly following the 3-Month Visit. If the subject reports inadequate pain relief, they will come in for an unscheduled visit.

Statistics
	
Only subjects who are implanted and have their devices activated will be included in the evaluation of the primary and secondary endpoints. The study sample size is based on the desired precision for the characterization of the secondary objectives. A sample size of 100 subjects provides a 95% confidence interval within 9.6% of the responder rate estimate, if the observed responder rate is 50%. For the primary objective, a sample size of 100 subjects ensures over 99% power to test a significant change from 0 under the following assumptions: two-sided alpha = 0.05, assumed mean reduction = 20 with a standard deviation = 30. Globally up to 215 subjects will be enrolled to ensure at least 100 subjects are implanted, have their devices activated, and are followed through the 3-Month Visit.
 
The primary objective analysis will test the average change in overall pain from Baseline to the 3-Month Visit against no change, using a two-sided, one sample t-test with alpha = 0.05.
 
The secondary objectives are not alpha-controlled; they will be characterized but not evaluated with statistical testing.

